Visit window	NA	-	± 3 d	± 3 d	± 3 d	± 3 d	± 1 wk	± 1 wk	± 1 wk	± 1 wk
Informed consent	X									
Demography	X									
Medical and surgical history ⁷	X									
Eligibility	X	X								
Tumor biopsy ⁸	X				X ³¹					
Performance (ECOG) status ⁹	X	X	X	X		X ³²	X	X	X	X
Height ⁹	X									
Weight ⁹	X	X	X	X		X ³²	X	X		
Physical examination ⁹	X	X	X	X		X ³²	X	X	X	
Vital signs ¹⁰	X				PRE- & 15m, 30m, 1h, 2h, 4h POST-dose		X	X		
Electrocardiogram ¹¹	X	PRE- & 30 min POST-dose	PRE- & 30 min POST-dose	PRE- & 30 min POST-dose		X ³²				
Hematology and biochemistry ¹²	X	X		X		X ³²	X			
Creatinine clearance ¹³	X	X	X							
Coagulation ¹²	X	X	X	X		X ³²				

List of footnotes

1. Re-screening may be allowed on a case-by-case basis. In the case of out-of-range laboratory results during the screening period, a re-test may be allowed within the screening period. The investigator must contact the medical monitor to discuss each re-screening case.
2. The EoT visit will be done within 7 days after the subject is taken off CyPep-1.

3. The FU visit will occur at least 30 days after the last CyPep-1 or pembrolizumab (combination arm) administration (if the EoT visit occurs more than 30 days after the last treatment administration, the FU visit will be skipped).
4. For subjects who leave the trial early and do not receive any other anti-cancer therapy or any other investigational therapy, PFS visits should continue to be performed every 8 weeks (from D1) until occurrence of confirmed progressive disease (PD) or until start of any further line of anticancer treatment.
5. Every 3 months after confirmed PD and until the end of the trial, by phone call. In case of unconfirmed PD (iUPD) by iRECIST and subject has started further line of anti-cancer treatment, the first OS-FU visit will be done 90 days after the iUPD event occurred. Besides overall survival status, any next line of anti-cancer therapies, ORR and duration of response to next line anti-cancer therapies, and additional relevant information will be recorded. If necessary, patients may be contacted occasionally outside of this FU window, and data regarding next line anti-cancer therapies can be collected, retrospectively.
6. Additional cycles of CyPep-1 are planned with continued Q2W administration, please see [Table 1 b/e](#) for schedule of assessments (in this case, end of treatment [EoT], FU, PFS-FU, and OS-FU are relative to each cycle).

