24. Continuous Q2W CyPep-1 treatment is planned and until confirmed PD, unacceptable toxicity or consent withdrawal, loss to follow up, or trial end, whichever occurs first. Lesions not originally planned to be injected with CyPep-1 at screening may also be injected per investigator's discretion, if necessary and after consulting with medical monitor. Follow-up visits will follow the interval as defined in **Table 1a/c**. For subjects in the combination arm treatment with pembrolizumab will continue as per SoC following Q6W dosing until PD, unacceptable toxicity or consent withdrawal.

25. Per additional cycles: C2, C3, ...Cn. CXV1 is scheduled 2 weeks after the last CyPep-1 administration (to follow a Q2W administration schedule).

26. If a subject is receiving additional Q2W treatment with CyPep-1, a biopsy of any new injected lesion(s) can be taken (not mandatory) after 6 weeks for each subsequent cycle. A biopsy at CxD1 (pre-dose) is only applicable if any new lesion(s) are selected for CyPep-1 injection (not mandatory). Arrangements to be made for any tumor material to be sent for analysis are described in the laboratory manual. The visit window for biopsies on CxV4 is ± 3 days.

27. Cytokine levels should only be assessed in the first and second cycles of CyPep-1 administration.

28. The visit window for biopsies on C1V4 is ± 3 days.

29. Pembrolizumab administration only in the combination arm (Arm B). Pembrolizumab should be administered as per SOC Q6W independent of other administrations or assessments (see **Section 5.3.2** for details regarding pembrolizumab administration). CyPep-1 should be administered 30 to 60 min after pembrolizumab if on the same day. All safety assessments and safety laboratory testing should be performed on all pembrolizumab administration days as specified in **Table 1c**. Pembrolizumab will be administered using IV infusion after all procedures and assessments have been completed. See **Section 5.3.6.2** for dose modifications and toxicity management. Pembrolizumab will be administered to a maximum of 18 cycles and then stopped.

30. Thyroid panel should include: triiodothyronine (T3) or free triiodothyronine (FT3); free thyroxine (FT4); thyroid stimulating hormone (TSH).

31. The frequency for tumor biopsy is every 6 weeks from D1 if a subject stays on treatment. The biopsy of at least one injected lesion is highly desired but not mandatory.

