To minimize the risks to subjects upon administration of pembrolizumab, the following measures are recommended, depending on the situation ([Sections 5.3.6.2](#) and [5.3.6.3](#) for complete list of considerations on dose modification of pembrolizumab based on the occurrence and severity of immune- or infusion-related AEs):

- Suspected Stevens-Johnson syndrome or toxic epidermal necrolysis: withhold until recovery to Grades 0-1; if this does not occur within 12 weeks after last dose of pembrolizumab or if corticosteroid dosing cannot be reduced to ≤ 10 mg prednisone or equivalent per day within 12 weeks, pembrolizumab should be permanently discontinued.
- Confirmed Stevens-Johnson syndrome or toxic epidermal necrolysis: permanent drug discontinuation.
- Grade 3 or 4 myocarditis, encephalitis, or Guillain-Barre syndrome: withhold until recovery to Grades 0-1 or, if above conditions apply, permanently discontinue.

Phase IIa Arm B:

CyPep-1 monotherapy can continue if there is unacceptable toxicity to pembrolizumab. Pembrolizumab monotherapy can continue if there is unacceptable toxicity to CyPep-1. Related dose modification rules for CyPep-1 and pembrolizumab is detailed in [Section 5.3.6](#)).

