5.3.5 Duration of the Treatment Regimen

Intratumoral CyPep-1

Each subject will undergo up to 4 weeks of screening, followed by a DLT/TLT observation period of 6 weeks (5 weeks of CyPep-1 treatment plus 1 week observation). In absence of DLT/TLTs, treatment continues with Q2W intratumoral injections of CyPep-1 until confirmed PD, unacceptable toxicity, death, withdrawal of consent, loss to follow-up, or trial end, whichever occurs first. For Arm D, after screening, each subject will undergo QW CyPep-1 treatment until the second iRECIST/itRECIST assessment at week 16, followed by a Q2W dosing scheme until confirmed PD, unacceptable toxicity, death or consent withdrawal, loss to follow-up, or trial end, whichever occurs first.

Pembrolizumab (intravenous)

Pembrolizumab will be administered as specified in Section [5.3.2](#).

In case a subject discontinues treatment with CyPep-1 in the combination arm (Arm B) and the subject remains eligible to participate in the trial after review by the Investigator and medical monitor, pembrolizumab treatment is planned to continue at Q6W as per institutional guidelines until PD, unacceptable toxicity, death, or consent withdrawal for a maximum of 18 treatment cycles. All assessments continue to be reported as per the schedule of assessments.

In case a subject discontinues with pembrolizumab in the combination arm (Arm B) and the subject remains eligible to participate in the trial after review by the Investigator and medical monitor, CyPep-1 treatment is planned to continue at Q2W until PD, unacceptable toxicity, death, or consent withdrawal. All assessments continue to be reported as per the schedule of assessments.

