8.3 Reference Dates

The following reference dates are defined:

1. **Screening date** is defined as the eCRF provided date on which a subject was screened for trial entry. If screening procedures took several days, the first of these days is considered as screening date.
2. **Informed consent date** is defined as the date of Informed Consent signed by the subject collected on Informed Consent eCRF page.
3. **Treatment start date(time)** is defined as the date(time) of first dose of any study drug (Cy-Pep1 or pembrolizumab). **CyPep-1 treatment start date(time)** is defined as the date(time) of first dose of CyPep-1. **Pembrolizumab treatment start date(time)** is defined as the date(time) of first infusion of pembrolizumab.
4. **Treatment end date(time)** is defined as the date(time) of last dose of any study drug (Cy-Pep1 or pembrolizumab). **CyPep-1 treatment end date(time)** is defined as the date(time) of last dose of CyPep-1. **Pembrolizumab treatment end date(time)** is defined as the end date(time) of last infusion of pembrolizumab.
5. **End of study date** is defined as Date of study completion/discontinuation recorded on the End of Study Form in the eCRF.

Statistical Analysis Plan

SMS-0571/CyPep-1

V3.0 Final

04-Jun-2024

6. Age will not be calculated and will come directly from the eCRF. The eCRF uses the demographics assessment date at Screening as its reference date for age calculation.
7. Safety data, such as AEs and laboratory assessments, will use the treatment start date as a reference date.
8. Efficacy data will use the treatment start date as a reference date.
9. **Study day** will be based on treatment start date as a reference date.

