8.5 Study Time Periods

Where applicable, data reporting will be classified by the following study periods for analysis:

1. **Pre-treatment** is defined as the period prior to a subject's treatment start date(time). Assessments done on treatment start date before treatment start per protocol, but where assessment start time is not collected on eCRF, are considered to occur pre-treatment; this is applicable for physical examination and ECOG assessments.
2. **On-treatment** is defined as the period between a subject's treatment start date(time) and End of Treatment visit date (both date(time)s inclusive). In case EoT visit does not occur due to death, withdrawal of consent or loss to follow-up, subject's end of on-treatment period is considered to occur at date of death, date of withdrawal of consent or date lost to follow-up, respectively.
3. **Post-treatment** is defined as the period following the on-treatment period.

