11.4 Clinical Laboratory Evaluation

Laboratory tests will be performed at times defined in the protocol Schedule of Assessments. Biochemistry, hematology, and coagulation parameters will be reported based on the International System of Units (SI). All clinical laboratory data collected during the on-treatment period will be presented for the SAF by visit, timepoint and cohort/arm, as applicable. Data collected during the pre-treatment and post-treatment periods will only be listed.

The following laboratory evaluations will be reported in data summaries:

1. **Hematology:** parameters to be assessed include hemoglobin, hematocrit, red blood cell (RBC) count, white blood cell (WBC) count with differential count (neutrophils, eosinophils, basophils, lymphocytes, monocytes), and platelet count. Neutrophil-to-lymphocyte count will additionally be derived.

Statistical Analysis Plan

SMS-0571/CyPep-1

V3.0 Final

04-Jun-2024

2. **Biochemistry:** parameters to be assessed include creatinine, alkaline phosphatase, phosphate, total bilirubin, direct bilirubin (only applicable if total bilirubin levels $> 1.5 \times \text{ULN}$ [upper limit of normal]), ALT (alanine transaminase), AST (aspartate transaminase), gamma-glutamyl transferase, total protein, albumin, uric acid, urea, sodium, potassium, calcium, chloride, glucose, lactate dehydrogenase, amylase, lipase, creatinine phosphokinase, cholesterol and triglycerides. Creatinine clearance will be estimated by the CKD-EPI and the Cockcroft-Gault formula.
3. **Coagulation:** parameters to be assessed include prothrombin time (PT), international normalized ratio (INR), and activated partial thromboplastin time (APTT).
4. **Urinalysis:** parameters to be assessed include leukocytes, nitrite, pH, protein, glucose, ketones, urobilinogen, bilirubin, occult blood (hemoglobin and erythrocytes) (dipstick). If abnormal, sediment will be performed (including WBC, RBC, epithelial cells, crystals, casts, bacteria, other).
5. **Thyroid function:** free T3, free T4, T3 and TSH.

Observed values and changes from baseline for hematology, biochemistry and coagulation laboratory evaluations will be summarized at each visit; maximum and minimum most extreme change will be summarized as well.

Urinalysis parameters will be summarized at each visit using the number (%) of subjects with results of normal; abnormal, not clinically significant; abnormal, clinically significant.

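### Arm B: the SAP's on-treatment period can end while pembrolizumab is still being given, so laboratory, vital-sign, ECG and ECOG data from that time leave the by-visit and most-extreme-change summaries

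*Protocol*

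**What the plan says.** **Protocol.** Footnote 2 of the Schedule of Assessments reads "The EoT visit will be done within 7 days after the subject is taken off CyPep-1". It is attached to the EoT column of the Arm B table (Table 1c) as well as to the monotherapy tables, and there is no Arm B variant.

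Staying on pembrolizumab after CyPep-1 has stopped is a foreseen path. Section 1.9.3 states "Pembrolizumab monotherapy can continue if there is unacceptable toxicity to CyPep-1". Section 5.3.5 says that, after review, "pembrolizumab treatment is planned to continue at Q6W as per institutional guidelines until PD" or another stopping reason, to a maximum of 18 cycles, and adds "All assessments continue to be reported as per the schedule of assessments". Footnote 29 requires that "All safety assessments and safety laboratory testing should be performed on all pembrolizumab administration days". Tables 1c and 1d schedule thyroid tests every 6 weeks on trial treatment.

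**SAP.** Section 8.5 defines on-treatment as the time between "treatment start date(time) and End of Treatment visit date (both date(time)s inclusive"). It gives a substitute end date only when the EoT visit does not take place because of death, withdrawal of consent or loss to follow-up. Everything later is post-treatment. On laboratory data, section 11.4 states "Data collected during the pre-treatment and post-treatment periods will only be listed". Sections 11.5.1 (vital signs and weight), 11.5.2 (ECG) and 11.5.4 (ECOG) have the same rule. Section 8.6 limits most extreme change to on-treatment assessments. Section 8.3, however, has a treatment end date that "is defined as the date(time) of last dose of any study drug (Cy-Pep1 or pembrolizumab").

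**The concern.** Taken together, these rules class a subject who is still receiving pembrolizumab as post-treatment once the CyPep-1 EoT visit has been held. The data are still collected, but they move from the summaries to the listings.

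Safety of the combination is a primary objective (Protocol 2.1.1), and additional safety parameters are part of the primary endpoint (Protocol 2.2.1). Protocol 5.3.6.2 warns that immune-related events may appear at any time from shortly after the first pembrolizumab dose to several months after the last. The liver and thyroid tests made on continued pembrolizumab are among those intended to detect them. The exposure tables in SAP 9.6.2 would count the later infusions, while the by-visit safety summaries would omit the results that go with them.

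**Working it through.** The plan states no figure to reproduce. The check traces the definitions and then counts days.

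**1. Is footnote 2 shorthand for both drugs?** The text does not say so. Footnote 3, the next line, names CyPep-1 or pembrolizumab for the combination arm, and footnote 2 names CyPep-1 only. The problem runs one way: a subject who stops pembrolizumab and stays on CyPep-1 remains on-treatment.

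**2. How does the SAP class the later data?** The EoT visit falls within 7 days of coming off CyPep-1. On-treatment ends on that date (SAP 8.5), and no exception covers continued pembrolizumab. Treatment itself ends at the last infusion (SAP 8.3). Between the two dates the subject is both under treatment and post-treatment.

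**3. Which outputs are affected?**

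| Output | SAP wording | Data after EoT |
|---|---|---|
| By-visit laboratory, vital signs, weight, ECG, ECOG | on-treatment data presented, the rest listed (11.4, 11.5.1, 11.5.2, 11.5.4) | excluded |
| Most extreme change | on-treatment only (8.6) | excluded |
| Shift tables, worst grade, hepatotoxicity | worst or maximum post-baseline (8.16, 11.4, 11.5.2, 11.5.4) | ambiguous |
| CTCAE toxicities at any time; markedly abnormal vital signs overall | no period stated (11.4, 11.5.1) | ambiguous |
| Adverse event tables | every event after first dose of either drug (11.1) | included |
| Listings | all data | included |

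The ambiguous rows arise because SAP 8.6 defines a post-baseline value as one collected after treatment start and gives no end date, while the listing-only sentences are general. Two programmers could produce different shift tables from the same text. Thyroid results enter through the CTCAE tables, so they are excluded by visit and ambiguous for the worst grade.

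**4. How long can the gap be?** Inputs: pembrolizumab every 6 weeks, maximum 18 doses (Protocol 5.3.2), and EoT at most 7 days after CyPep-1 stops (footnote 2). Assumptions: all 18 doses are given on schedule, the subject is taken off CyPep-1 on the day of its last dose, and EoT is held 7 days later.

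Infusion days are 1 + 42k for k = 0 to 17. The last is 1 + 42 × 17 = Day 715. The gap is 715 − (last CyPep-1 day + 7).

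| Last CyPep-1 | EoT | Infusions after EoT | EoT to last infusion |
|---|---|---|---|
| Day 29 | Day 36 | 17 of 18 | 715 − 36 = 679 days (97 weeks) |
| Day 169 | Day 176 | 13 of 18 | 715 − 176 = 539 days (77 weeks) |
| Day 337 | Day 344 | 9 of 18 | 715 − 344 = 371 days (53 weeks) |

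One affected subject is 1/15 = 6.7% of the planned arm.

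**The case against.** The strongest reply is that the main safety routes do not depend on the on-treatment period. Every adverse event after the first dose of either drug is treatment-emergent, with no cut-off (SAP 11.1). Clinically relevant laboratory abnormalities must be recorded as adverse events (Protocol 7.2.2). Arm B events are reported through 30 days after study treatment ends, and serious events through 90 days, or 30 days if new anticancer therapy starts (Protocol 7.2.1.3). The SAP also provides a listing of Grade 3 or higher laboratory abnormalities and a by-subject table-listing of worst severity (11.4). All of this stands, and it limits the damage.

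A reader might infer that the data drop out of every safety summary. The documents do not support that. Adverse event tables are untouched, and the scope of the shift and worst-grade outputs is open.

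A reader might also infer that Arm B will look safer than it is. A maximum over fewer values cannot be larger, but that does not establish the claim. The number of subjects affected is unknown and may be zero. An event that makes a subject stop CyPep-1 comes before EoT and is tabulated among events leading to discontinuation (SAP 11.1.3). A treatment-related toxicity that causes discontinuation in Cycle 1 is itself a treatment-limiting toxicity (Protocol 3.1.2).

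Two readings of size should also be resisted. Multiplying 17 infusions by 6 weeks gives 102 weeks, but that counts time after the last infusion. Nor does an affected subject remove 6.7% of the arm: data up to EoT are kept, and the subject stays in the any-time CTCAE denominator.

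Sites may in practice hold EoT only after both drugs have stopped, and the gap would then vanish. No passage says so.

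**Conclusion.** The point holds as a misclassification in the SAP's period definition. For an Arm B subject who stops CyPep-1 first, the by-visit and most-extreme-change summaries omit laboratory, vital-sign, weight, ECG and ECOG data collected during continued pembrolizumab. For shift, worst-grade, hepatotoxicity and any-time outputs the SAP does not settle whether those data count. The data remain in the listings, and adverse event reporting is complete.

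The upper-end illustration is 17 of 18 infusions and about 97 weeks. It needs an early CyPep-1 stop followed by full pembrolizumab, in subjects who had already progressed on anti-PD-1/L1 treatment (Protocol 4.1, criterion 23), so typical gaps may be much shorter. How many of the 15 planned subjects are affected cannot be derived from the documents. The conclusion rests on taking footnote 2 and SAP 8.5 as written.

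**What to change.** **SAP 8.5.** End the on-treatment period at the later of (a) the EoT visit date and (b) the SAP 8.3 treatment end date, that is, the last dose of any study drug, plus the 7-day EoT window. Keep the existing rule for death, withdrawal and loss to follow-up. State in 8.6 or 8.16 that the shift, worst-grade, any-time and hepatotoxicity outputs use the same period.

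**Protocol.** Footnote 2 must be reconciled with section 5.3.5 and with footnotes 3, 6 and 21. Footnotes 3 and 21 measure timing from the last dose of either drug, and footnote 6 describes EoT as relative to each cycle. When the visit should take place is for the sponsor to decide. A change to it would be a protocol amendment, and the analysis does not need to wait for one.

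**Cost.** One sentence in SAP 8.5, one clarifying sentence for the outputs, and one derived date in programming. No dose, visit or data collection changes. In the other arms the rule can lengthen the period by at most 7 days, where EoT was held early; it can be limited to Arm B if that is unwanted.
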